**Table 1. Schedule of Activity (Cohort 1-Oral [C]-PF-07220060 Administration)**

Visit Identifier Abbreviations used in this table may be found in Appendix 10	Screen a		Study Period														FU phone call	Early Termination/ Discontinuation	
Days relative to Day 1	Days (-28 to -2)	Day -1	Day 1										Day 2		Day 3	Day 4	Day 5-14 b	Day 29- 36	
Hours After Oral [  C]-PF-07220060 Dose	-	-	0	0.5	1	2	3	4	6	8	12	16	24	36	48	72	96-312	-	-

- h. PF-07220060 will be administered orally after overnight fasting of at least 10 hours on Day 1.
- i. Questionnaire to be completed by participants as soon as practically possible (within 1 min) after completion of dosing, plus at 5 min, 10 min, and 20 min post dose. PK samples will take the priority when the 2 procedures conflict.
- j. Vomitus samples will be collected as described in [Section 8.5.3](#).
- k. Blood samples will be collected at predose (within approximately 1 hour prior to PF-07220060 dosing) and at post-dose time points indicated in the table up to discharge. If ECG and blood pressure/pulse rate assessments are scheduled at the same nominal time point as a PK sample, PK samples should be collected after completion of these assessments, with blood sampling for PK as close as possible to the planned timepoint. Blood samples will be processed to plasma as per instructions of the lab manual. (See also [Section 8.5.1](#)).
- l. This 8 mL screening sample collection will not be used to analyze the cold PF-07220060 but will be used to assess C total radioactivity for screening and be stored for potential use as the diluent for post-dose AMS samples.
- m. Blood samples (approximately 10 mL) will be collected at predose (within approximately 1 hour prior to PF-07220060 dosing) and at 0.5, 1, 2, 4, 6, 8, 12, 24, 48, 72, 96, and 144 (if still in CRU) hours post-dose. If ECG and blood pressure/pulse rate assessments are scheduled at the same nominal time point as these samples, these samples should be collected after completion of these assessments, with blood sampling for PK as close as possible to the planned timepoint. Blood samples will be processed to plasma as per instructions of the lab manual. (See also [Section 8.5.1](#)).
- n. HbsAb will be tested if HbsAg and/or HbcAb are positive.
- o. If not collected on the designated collection day, collect at the next available time point when biospecimens are being collected in conjunction with a participant visit.
- p. Urine drug and urine cotinine (mandatory) and alcohol breath test or urine alcohol test or blood alcohol test (at discretion of investigator) will be performed at screening, on Day -1. These tests may be performed at any other time at the discretion of the investigator.
- q. "Blank" predose urine sample to be collected within 24h prior to dosing and at intervals of 0-12h, 12-24h post oral dose, and at each subsequent 24h interval up to discharge. Forced void into the collection container at the end of the collection period. (see also [Section 8.5.2](#)).
- r. "Blank" fecal sample to be collected at baseline from at least 1 bowel movement during the 48h predose interval, which may be collected from home. The last collected fecal sample will be used as the pre-dose sample and all previous pre-dose samples will be destroyed. Fecal samples will also be collected at intervals of 0-24 h post oral dose, and at each subsequent 24h interval up to discharge. (see also [Section 8.5.2](#)).

**Table 2. Schedule of Activity (Cohort 2-Oral unlabeled PF-07220060 and IV [C]-PF-07220060 administration)**

Visit Identifier	Screen a		Study Period																	FU phone call	Early Termination/ Discontinuation
Abbreviations used in this table may be found in Appendix 10																					
Days relative to Day 1	Day (-28 to -2)	Day -1	Day 1												Day 2	Day 3	Day 4	Day 5-14 b	Day 29-36		
Hours Relative to Oral Dosing of Unlabeled PF-07220060	-	-	0	0.5	1	2	2.5	2.75	3	4	6	8	12	16	24	36	48	72	96-312	-	-
Hours Relative to Dosing of [  C]-PF-07220060 (IV infusion start)						0	0.5	0.75	1	2	4	6	10	14	22	34	46	70	94-310		-
Informed consent	X																				
Review of eligibility criteria	X	X																			
Inpatient stay at CRU		X	→	→	→	→	→	→	→	→	→	→	→	→	→	→	→	→	X b		X
Medical history	X	X																			
Demography c	X																				
Review drug, alcohol/tobacco use d	X	X																	X e	X	X
Review prior and concomitant medications	X	X	→	→	→	→	→	→	→	→	→	→	→	→	→	→	→	→	X	X	X
Physical examination f	X	X																	X e		X
Supine 12-lead ECG (single)	X		X							X									X e		X
Supine vital signs (blood pressure and pulse rate)	X		X							X									X e		X
Contraception Check g	X	X																		X	X
Serious and non-serious adverse event monitoring	X	X	→	→	→	→	→	→	→	→	→	→	→	→	→	→	→	→	X	X	X
Oral Unlabeled PF-07220060 administration h			X																		
IV infusion of [  C]-PF-07220060						X i															
Taste assessment j			X a																		
Emesis collection for radioactivity measurement, if occurs k			X	→	→	→	→	→	→	→	→	→	→	→	X	→	X	X			
Blood Samples for																					
PK of PF-07220060 [LCMS] l			X	X	X	X			X	X	X	X	X	X	X	X	X	X	X		X
PK of [  C]PF-07220060 m	X					X	X	X	X	X	X	X	X	X	X	X	X	X	X		X

**Table 2. Schedule of Activity (Cohort 2-Oral unlabeled PF-07220060 and IV [C]-PF-07220060 administration)**

Visit Identifier	Screen a		Study Period																FU phone call	Early Termination/ Discontinuation	
Abbreviations used in this table may be found in Appendix 10																					
Days relative to Day 1	Day (-28 to -2)	Day -1	Day 1												Day 2	Day 3	Day 4	Day 5-14 b	Day 29-36		
Hours Relative to Oral Dosing of Unlabeled PF-07220060	-	-	0	0.5	1	2	2.5	2.75	3	4	6	8	12	16	24	36	48	72	96-312	-	-
Hours Relative to Dosing of [  C]-PF-07220060 (IV infusion start)						0	0.5	0.75	1	2	4	6	10	14	22	34	46	70	94-310		-
Metabolite identification			X	X	X	X				X	X	X	X		X		X	X	X b,n		
Clinical laboratory after ≥4hour fast	X	X															X		X e		X
Serology: HBsAg, HBsAb, HBcAb, HCVAb, and HIV o	X																				
Research Sample for Pharmacogenomics p			X p																		
Urine samples for																					
Drug test q	X	X																			
Cotinine test q	X	X																			
Spot collection for urinalysis (and microscopy, if needed)	X	X													X				X e		X
Total  C radioactivity/Metabolite identification r		X				X	→	→	→	→	→	→	→	X	→	X	→	X	X	X	
Feces samples for																					
Total  C radioactivity/Metabolite identification s		X				X	→	→	→	→	→	→	→	→	X	→	X	X	X		

- a. Screening will be performed within 28 days prior to the single oral dose of PF-07220060.
- b. See [Section 4.1](#) for details on Cohort 2 discharge criteria.
- c. Demographics will include participant race, ethnicity, age, gender, height, and weight during the screening visit.
- d. The review of drug, alcohol/tobacco use may include an alcohol breath test or urine alcohol test or blood alcohol test (at discretion of investigator), which will be performed at screening, on Day -1 and at discharge. These tests may be performed at any other time at the discretion of the investigator.
- e. Procedures to be performed only on the day of discharge or Day 14. No ECG or vital signs will be collected on Day 14. (see also [Section 4.1](#)).
- f. Complete physical exam including height and weight will be performed by trained medical personnel at the CRU at screening or Day -1 only. A brief physical examination may be performed prior to discharge from the CRU and at other designated time points at the discretion of the investigator.

**Table 2. Schedule of Activity (Cohort 2-Oral unlabeled PF-07220060 and IV [C]-PF-07220060 administration)**

Visit Identifier	Screen a		Study Period																FU phone call	Early Termination/ Discontinuation	
Abbreviations used in this table may be found in Appendix 10																					
Days relative to Day 1	Day (-28 to -2)	Day -1	Day 1												Day 2	Day 3	Day 4	Day 5-14 b	Day 29-36		
Hours Relative to Oral Dosing of Unlabeled PF-07220060	-	-	0	0.5	1	2	2.5	2.75	3	4	6	8	12	16	24	36	48	72	96-312	-	-
Hours Relative to Dosing of [  C]-PF-07220060 (IV infusion start)						0	0.5	0.75	1	2	4	6	10	14	22	34	46	70	94-310		-

- g. The investigator or his/her designee will discuss with the participant the need to use highly effective contraception consistently and correctly according to contraception guidelines.
- h. PF-07220060 will be administered orally after overnight fasting of at least 10 hours on Day 1.
- i. IV [C]PF-07220060 dose to be administered as an infusion over approximately 30 minutes (starting at approximately 2 hour after the administration of the oral unlabeled PF-07220060 dose).
- j. Questionnaire to be completed by participants as soon as practically possible (within 1 min) after completion of dosing, plus at 5 min, 10 min, and 20 min post dose. PK samples will take the priority if the 2 procedures start to conflict.
- k. Vomitus samples will be collected as described in [Section 8.5.3](#).
- l. Blood samples (approximately 4 mL) will be collected at pre dose (within approximately 1 hour prior to PF-07220060 dosing) and at post-dose time points indicated in the table up to discharge. If ECG and blood pressure/pulse rate assessments are scheduled at the same nominal time point as a PK sample, PK samples should be collected after completion of these assessments, with blood sampling for PK as close as possible to the planned timepoint. Blood samples will be processed to plasma as per instructions of the lab manual. (See also [Section 8.5.1](#)).
- m. A 8 mL screening sample collection will be used to assess [C]PF-07220060 for screening only and will be stored for potential use as the diluent for post-dose AMS samples. Blood samples (approximately 4 mL) will be collected at preinfusion (within approximately 15 min prior to [C]PF-07220060 infusion) and at post-infusion time points indicated in the table up to discharge. If ECG and blood pressure/pulse rate assessments are scheduled at the same nominal time point as a PK sample, PK samples should be collected after completion of these assessments, with blood sampling for PK as close as possible to the planned timepoint. Blood samples will be processed to plasma as per instructions of the lab manual. (See also [Section 8.5.1](#)).
- n. Cohort 2 blood samples (approximately 10 mL) for contingent use will be collected at predose (within approximately 1 hour prior to PF-07220060 dosing) and at 0.5, 1, 2, 4, 6, 8, 12, 24, 48, 72, 96, and 144 (if still in CRU) hours post-dose. If ECG and blood pressure/pulse rate assessments are scheduled at the same nominal time point as these samples, these samples should be collected after completion of these assessments with blood sampling for PK as close as possible to the planned timepoint. Blood samples will be processed to plasma as per instructions of the lab manual. (See also [Section 8.5.1](#)).
- o. HBsAb will be tested if HBsAg and/or HBcAb are positive.
- p. If not collected on the designated collection day, collect at the next available time point when biospecimens are being collected in conjunction with a participant visit.
- q. Urine drug and urine cotinine (mandatory) and alcohol breath test (at discretion of investigator) will be performed at screening, on Day -1. These tests may be performed at any other time at the discretion of the investigator.

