**Prior/Concurrent Clinical Study Experience:**

6. Previous administration with an investigational product (drug or vaccine) within 30 days (or as determined by the local requirement) or 5 half-lives (whichever is longer) preceding the first dose of study intervention used in this study. Previous exposure to PF-07220060 or participation in studies requiring PF-07220060 administration.
7. Participants enrolled in a previous radionucleotide study or who have received radiotherapy within 12 months prior to screening or such that total radioactivity would exceed acceptable dosimetry.

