**Diagnostic Assessments:**

8. A positive urine drug test. A single repeat for positive drug screen may be allowed.
9. Screening supine BP  $\geq 140$  mm Hg (systolic) or  $\geq 90$  mm Hg (diastolic) for participants  $< 60$  years; and  $\geq 150/90$  mm Hg for participants  $\geq 60$  years old, following at least 5 minutes of supine rest. If BP is  $\geq 140$  mm Hg (systolic) or  $\geq 150$  mm Hg (based on age) or  $\geq 90$  mm Hg (diastolic), the BP should be repeated 2 more times and the average of the 3 BP values should be used to determine the participant's eligibility.
10. Standard 12-lead ECG that demonstrates clinically relevant abnormalities that may affect participant safety or interpretation of study results (eg, QTcF  $> 450$  ms, complete LBBB, signs of an acute or indeterminate- age myocardial infarction, ST-T interval changes suggestive of myocardial ischemia, second- or third- degree AV block, or serious bradyarrhythmias or tachyarrhythmias). If QTcF exceeds 450 ms, or QRS exceeds 120 ms, the ECG should be repeated twice and the average of the 3 QTcF or QRS values is used to determine the participant's eligibility. Computer-interpreted ECGs should be overread by a physician experienced in reading ECGs before excluding a participant.
11. Total  $^{14}\text{C}$  radioactivity measured in plasma exceeding 11 mBq/mL.
12. Participants with ANY of the following abnormalities in clinical laboratory tests at screening, as assessed by the study-specific laboratory and confirmed by a single repeat test, if deemed necessary:
  - ALT, AST, bilirubin  $\geq 1.05 \times \text{ULN}$ ; participants with a history of Gilbert's syndrome may have direct bilirubin measured and would be eligible for this study provided the direct bilirubin level is  $\leq \text{ULN}$ ;
  - eGFR  $< 60$  mL/min/1.73 m^2 based on the 2021 CKD-EPI (combined serum creatinine plus serum cystatin C) equation;
  - Blood calcium or potassium  $< 0.9 \times \text{LLN}$  or  $> 1.1 \times \text{ULN}$ ;

- Absolute neutrophil count  $<0.8 \times \text{LLN}$ .

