## 8.5. Pharmacokinetics

### 8.5.1. Plasma for Pharmacokinetic Analysis of Total $^{14}\text{C}$ Radioactivity, PF-07220060, [ $^{14}\text{C}$ ]-PF-07220060 and Metabolic Profiling

Blood samples of approximately 8 mL, will be collected into appropriately labeled tubes containing  $\text{K}_2\text{EDTA}$  for measurement of total  $^{14}\text{C}$  radioactivity by AMS and PF-07220060 by LCMS in Cohort 1 as specified in the SoA. The 8 mL screening blood sample will be used to assess  $^{14}\text{C}$  total radioactivity for screening only and will be stored for potential use as the diluent for post-dose AMS samples. Blood samples of approximately 10 mL, will be collected into appropriately labeled tubes containing  $\text{K}_2\text{EDTA}$  for metabolite identification in Cohort 1 as specified in the SoA. Blood samples of approximately 4 mL, to provide a minimum of 1.5 mL plasma, will be collected for measurement of PF-07220060 by LCMS in Cohort 2 as specified in the SoA. Blood samples of approximately 4 mL, to provide a minimum of 1.5 mL plasma, will be collected for measurement of plasma concentrations of [ $^{14}\text{C}$ ]PF-07220060 by AMS in Cohort 2 as specified in the SoA. A 8 mL screening sample collection will be used to assess [ $^{14}\text{C}$ ]PF-07220060 for screening only and will be stored for potential use as the diluent for post-dose AMS samples. Blood samples of approximately 10 mL, will be collected into appropriately labeled tubes containing  $\text{K}_2\text{EDTA}$  for contingent use of metabolites identification in Cohort 2 as specified in the SoA. Instructions for the collection and handling of biological samples will be provided in the laboratory manual or by the sponsor. The actual date and time (24 hour clock time) of each sample will be recorded.

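### The Cohort 2 screening blood sample is assigned to labelled parent drug rather than total 14C, so no scheduled Cohort 2 measurement supports exclusion 11

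*Protocol*

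**What the plan says.** Protocol Section 5.2, criterion 11 (also in the synopsis) excludes anyone with total 14C "radioactivity measured in plasma exceeding 11 mBq/mL". It makes no distinction between cohorts. Section 8.1 requires the screening evaluations to confirm every eligibility criterion and allows no waivers.

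Both cohorts give an 8 mL blood sample at screening. For Cohort 1, Table 1 footnote l says that it will not be used for unlabelled drug "but will be used to assess 14 C total radioactivity for screening", and Section 8.5.1 agrees. For Cohort 2, Table 2 footnote m says "A 8 mL screening sample collection will be used to assess [ 14 C]PF-07220060 for screening only". The Cohort 2 sentence in Section 8.5.1 also assigns the sample to labelled "PF-07220060 for screening only and will be stored for potential use as the diluent for post-dose AMS samples". The screening mark in Table 2 sits on the [14C]PF-07220060 row, and the table has no row for total 14C in plasma.

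Section 5.2, criterion 6 excludes "Previous exposure to PF-07220060 or participation in studies requiring PF-07220060 administration".

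**The concern.** The criterion and the assay meant to serve it name different analytes. Total 14C is everything radioactive in the plasma. [14C]PF-07220060 is one compound, measured after chromatographic separation. A man carrying 14C from an earlier exposure would exceed the first without showing any of the second.

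What is at stake is a screen for residual 14C that is specified in one cohort and not in the other, when Fa is a ratio between the two. Under Sections 4.2 and 9.3.2.2, Cohort 1 supplies the numerator (urinary 14C after the oral dose) and Cohort 2 the denominator (urinary 14C after the IV dose). Undetected residual 14C in Cohort 2 would raise apparent IV recovery and push Fa down. Section 4.1 compares Fa, along with F, with 0.9 to judge permeability. With about 6 men per cohort, one affected man carries weight.

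**Working it through.** The plan gives no figure to reproduce. The check is mainly a comparison of passages.

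| Item | Cohort 1 | Cohort 2 |
|---|---|---|
| Exclusion 11 | total 14C in plasma, 11 mBq/mL | same |
| Screening analyte in schedule | total 14C (Table 1, footnote l) | [14C]PF-07220060 (Table 2, footnote m) |
| Screening analyte in Section 8.5.1 | total 14C | [14C]PF-07220060 |
| Row for total 14C in plasma | yes | none |

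1. Criterion 6 removes anyone previously exposed to the compound. Labelled parent should therefore be nil at screening in every eligible man, whatever his residual 14C.
2. A nil parent result cannot be compared with a limit on total 14C.
3. No other blood test scheduled at Cohort 2 screening measures 14C.
4. Followed literally, the schedule produces no Cohort 2 result for exclusion 11.

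**Scale of the effect on Fa.** This is illustrative only. The 14C dose is redacted, and the documents give no urinary 14C background, urine volume or IV urinary recovery. Assumptions: urine carries 14C at the plasma limit of 11 mBq/mL, 2 L/day, collection to 310 h after the start of infusion (the latest time in Table 2), 30% of the IV dose recovered in urine, true Fa 0.90, and no blank subtraction.

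- Background = 0.011 Bq/mL × 2,000 mL/day × (310/24) days ÷ 37 Bq/nCi = 7.7 nCi.
- As a percentage of an assumed dose of 100, 300 or 1,000 nCi, b = 7.7%, 2.6% or 0.8%.
- If all Cohort 2 men carried this, observed Fa = 0.90 × 30/(30 + b) = 0.72, 0.83 or 0.88.
- If one man in six did, the Cohort 2 geometric mean is multiplied by ((30 + b)/30)^(1/6) = 1.039, 1.014 or 1.004, and observed Fa = 0.90 divided by that = 0.87, 0.89 or 0.90.
- If collection stopped at 94 h, the background would be 0.011 × 2,000 × (94/24) ÷ 37 = 2.3 nCi, about 30% of the figure above.

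These numbers give scale; they do not estimate the harm from the wrong analyte. A man at exactly 11 mBq/mL would pass a correctly run screen in either cohort. Only 14C above the limit can be charged to the mismatch.

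**The case against.** The strongest reply is that this is a mislabelled analyte and everyone will know what is meant. The tube is drawn at screening for screening purposes, and exclusion 11 is the only criterion it could serve. Section 8.1 obliges the site to confirm that criterion. Section 8.5.1 also lets plasma samples taken for [14C]PF-07220060 be assayed for total 14C, and Section 8.1 lets a man who qualified for the earlier cohort without enrolling enter the later one without rescreening, so some Cohort 2 men may already have a total 14C result.

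Much of this stands. A reader might infer that exclusion 11 cannot be applied in Cohort 2. The documents do not support that: the sample exists and could be assayed for total 14C. But the re-use clause is discretionary, sets no timing before dosing and does not mention exclusion 11. A mandatory eligibility test should not depend on it.

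A reader might also infer that this screen is the only measured protection against residual 14C. It is not. Table 2 and Section 8.5.2 require predose urine and fecal blanks in Cohort 2, and the urine blank is in the matrix that Fa uses. The blank is not an eligibility check, however, and neither document says that it is subtracted: Protocol Table 4 and SAP Table 3 take urinary 14C from the observed data.

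Finally, the stored screening plasma may serve as AMS diluent, which suggests a contamination risk. That risk is marginal. Fa uses urine, and F uses parent measured after chromatographic separation. What remains is Cohort 2 total 14C in plasma, a tertiary endpoint measured only as needed.

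**Conclusion.** The contradiction is real. It appears in both the schedule and Section 8.5.1, and it is confined to Cohort 2. As written, the assay assigned to the Cohort 2 screening sample is uninformative for exclusion 11, and no other scheduled measurement supports that criterion. It is probably a drafting error, but it sits in the text that the site and laboratory will follow.

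The consequence for Fa is a possible downward bias of undetermined size. It needs a man with residual 14C above the limit who is not caught by the history-based exclusions (earlier radionuclide study or radiotherapy, occupational exposure), and urinary results reported without subtracting the blank. If the blank is subtracted, most of the effect goes. A reader might infer a definite bias in one arm only. The documents do not support this, since a correct screen still admits 14C up to 11 mBq/mL in both cohorts. The effect on conclusions is also softened: Section 4.2 calls Fa an approximation, and Section 4.1 uses the larger of F and Fa if F exceeds Fa. The correction is worth making because the gap is plain and closing it is cheap.

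**What to change.** - In Table 2, move the screening mark to a row for total 14C radioactivity, or relabel it, and reword footnote m so that the Cohort 2 screening sample is assessed for total 14C by AMS, matching Table 1 footnote l.
- Make the same change in the Cohort 2 sentence of Section 8.5.1.
- State that the result is checked against the 11 mBq/mL limit before Cohort 2 dosing.
- State in the SAP whether and how the predose urine blank is subtracted from urinary 14C, with the same rule in both cohorts.

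The cost is a few lines of text. The tube and volume do not change, and total 14C by AMS is already planned for the Cohort 1 screening sample.

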**Table 2. Schedule of Activity (Cohort 2-Oral unlabeled PF-07220060 and IV [C]-PF-07220060 administration)**

Visit Identifier Abbreviations used in this table may be found in Appendix 10	Screen a		Study Period																		FU phone call	Early Termination/ Discontinuation
Days relative to Day 1	Day (-28 to -2)	Day -1	Day 1												Day 2	Day 3	Day 4	Day 5-14 b	Day 29-36			
Hours Relative to Oral Dosing of Unlabeled PF-07220060	-	-	0	0.5	1	2	2.5	2.75	3	4	6	8	12	16	24	36	48	72	96-312	-	-	
Hours Relative to Dosing of [  C]-PF-07220060 (IV infusion start)						0	0.5	0.75	1	2	4	6	10	14	22	34	46	70	94-310		-	

- r. "Blank" predose urine sample to be collected within 24h prior to dosing and at intervals of 2-12h, 12-24h post oral dose, and at each subsequent 24h interval up to discharge. Forced void into the collection container at the end of the collection period. (see also [Section 8.5.2](#)).
- s. "Blank" fecal sample to be collected at baseline from at least 1 bowel movement during the 48h predose interval, which may be collected from home. The last collected fecal sample will be used as the pre-dose sample and all previous pre-dose samples will be destroyed. Fecal samples will also be collected at intervals of 2-24 h post oral dose, and at each subsequent 24h interval up to discharge. (see also [Section 8.5.2](#)).

